4.3.3 Treatment of Nivolumab or Ipilimumab-related infusion reactions

Since both nivolumab and ipilimumab contain only human immunoglobulin protein sequences, it is unlikely to be immunogenic and induce infusion or hypersensitivity reactions. However, if such a reaction were to occur, it might manifest with fever, chills, rigors, headache, rash, pruritus, arthralgias, hypotension, hypertension, bronchospasm, or other allergic-like reactions. All grade 3 or 4 infusion reactions should be reported within 24 hours to the study QAM and reported as an SAE if it meets the criteria. Infusion reactions should be graded according to NCI CTCAE (Version 4.03) guidelines.

Treatment recommendations are provided below and may be modified based on local treatment standards and guidelines, as appropriate:

NCI CTCAE Grade	Treatment	Premedication at subsequent dosing
Grade 1 Mild reaction; infusion interruption not indicated; intervention not indicated	Remain at bedside and monitor subject until recovery from symptoms.	The following prophylactic pre-medications are recommended for future infusions: 
 • Diphenhydramine 50 mg (or equivalent) and/or • Acetaminophen 325 to 1000 mg at least 30 minutes before additional nivolumab or ipilimumab administrations
Grade 2 Moderate reaction requires therapy or infusion interruption but responds promptly to symptomatic treatment [eg, antihistamines, non-steroidal anti- inflammatory drugs, narcotics, corticosteroids, bronchodilators, IV fluids]; prophylactic medications indicated for < 24 hours	Stop the nivolumab/ipilimumab infusion, begin an IV infusion of normal saline, and treat the subject with diphenhydramine 50 mg IV (or equivalent) and/or acetaminophen 325 to 1000 mg; Remain at bedside and monitor subject until resolution of symptoms. Corticosteroid and/or bronchodilator therapy may also be administered as appropriate. If the infusion is interrupted, then restart the infusion at 50% of the original infusion rate when symptoms resolve; if no further complications ensue after 30 minutes, the rate may be increased to 100% of the original infusion rate. Monitor subject closely. If symptoms recur, then no further nivolumab will be administered at that visit.	For future infusions, the following prophylactic pre-medications are recommended: 
 • Diphenhydramine 50 mg (or equivalent) and/or • Acetaminophen 325 to 1000 mg should be administered at least 30 minutes before nivolumab or ipilimumab infusions. If necessary, corticosteroids (up to 25 mg of SoluCortef or equivalent) may be used.
Grades 3 or 4	Immediately discontinue infusion of nivolumab/ipilimumab infusion.	No subsequent dosing

NU Study Number: NU 16B07
Other Study Number: CA 209-782

NCI CTCAE Grade	Treatment	Premedication at subsequent dosing

Severe reaction, Grade 3: prolonged [ie, not rapidly responsive to symptomatic medication and/or brief interruption of infusion]; recurrence of symptoms following initial improvement; hospitalization indicated for other clinical sequelae [eg, renal impairment, pulmonary infiltrates]. Grade 4: Life-threatening; pressor or ventilatory support indicated
	
Begin an IV infusion of normal saline and treat the subject as follows: Recommend bronchodilators, epinephrine 0.2 to 1 mg of a 1:1000 solution for subcutaneous administration or 0.1 to 0.25 mg of a 1:10,000 solution injected slowly for IV administration, and/or diphenhydramine 50 mg IV with methylprednisolone 100 mg IV (or equivalent), as needed.
 
Subject should be monitored until the Investigator is comfortable that the symptoms will not recur. Nivolumab or ipilimumab will be permanently discontinued. Investigators should follow their institutional guidelines for the treatment of anaphylaxis. Remain at bedside and monitor subject until recovery of the symptoms
 
In case of late-occurring hypersensitivity symptoms (eg, appearance of a localized or generalized pruritus within 1 week after treatment), symptomatic treatment may be given (eg, oral antihistamine or corticosteroids
	

4.4 Treatment with ipilimumab and or nivolumab beyond progression

In the event of an initial assessment of PD (based on RECIST Version 1.1), a subject may continue to receive the assigned study treatment as long as none of the criteria listed below are met. Criteria for discontinuation of investigational product include:

1. Confirmed PD: An initial assessment of PD by RECIST Version 1.1 will be confirmed by a repeat evaluation at the next tumor assessment time point, but no sooner than 4 weeks later (see Section 4.3.1 for disease evaluation).
2. Meets any of the other investigational product discontinuation criteria (Section 4.1.6)
3. Clinical symptoms or signs indicating significant PD such as the benefit-risk ratio of continuing therapy is no longer justified.
4. Decline in ECOG performance status.
5. Threat to vital organs/critical anatomical sites (eg, spinal cord compression) requiring urgent alternative medical intervention, and continuation of study therapy would prevent institution of such intervention.

If the lesions included in the tumor burden subsequently regress to the extent that the criteria for PD are no longer met, then treatment may continue according to the treatment schedule.

4.5 Concomitant Medications/Treatments

4.5.1 Permitted Medications

All treatments that the investigator considers necessary for a subject's welfare may be administered at the discretion of the investigator in keeping with the community standards of medical care. All concomitant medication will be recorded on the case report form (CRF) including all prescription, over-the-counter (OTC), herbal supplements, and IV medications and fluids. If changes occur during the trial period, documentation of drug dosage, frequency, route, and date may also be included on the CRF.

Subjects are permitted the use of topical, ocular, intra-articular, intranasal, and inhalational corticosteroids (with minimal systemic absorption). A brief (less than 3 weeks) course of corticosteroids for prophylaxis (eg, contrast dye allergy) or for treatment of non-autoimmune conditions (eg, delayed-type hypersensitivity reaction caused by a contact allergen) is permitted. Inhaled or topical steroids, and adrenal replacement steroid doses < 10 mg daily prednisone equivalent, are permitted in the absence of active autoimmune disease.

Concomitant palliative and supportive care for disease related symptoms (including bisphosphonates and RANK-L inhibitors) is allowed if initiated prior to first dose of study therapy.

Antihormonal therapy is permitted for patients with hormonal receptor positive IBC.

All concomitant medications received within 28 days before the first dose of trial treatment and 30 days after the last dose of trial treatment should be recorded. Concomitant medications administered after 30 days after the last dose of trial treatment should be recorded for SAEs.

4.5.2 Prohibited Medications

Subjects are prohibited from receiving the following therapies during the Screening and Treatment Phase of this trial:

- Anti-cancer systemic chemotherapy or biological therapy
- Immunotherapy not specified in this protocol
- Chemotherapy not specified in this protocol
- Investigational agents other than nivolumab or ipilimumab
- Radiation therapy
- Corticosteroids are not permitted unless they fall under the criteria listed in 4.5.1

4.6 Duration of Therapy

In the absence of treatment delays due to adverse event(s), treatment may continue until one of the following criteria applies:

- Disease progression (please refer to 4.4 for guidance regarding treatment beyond progression),
- Intercurrent illness that prevents further administration of treatment,
- Unacceptable adverse event(s) as already described in session.

4.7 Duration of Follow Up

All patients will be followed for adverse events for 12 weeks after last dose of nivolumab and or ipilimumab, or until the patient starts a new treatment, whichever occurs first. Patients who discontinue treatment for unacceptable adverse event(s) will be followed until resolution or stabilization of the adverse event (i.e. the grade is not changing). If a patient stops treatment due to unacceptable adverse event(s) but has not demonstrated

NU Study Number: NU 16B07
Other Study Number: CA 209-782

disease progression, then the patient will be followed with imaging studies every 8 weeks until the time of progression radiographically according to RECIST 1.1 criteria. In the event that a radiographic response is detected, then this event will be included as a response in the final analysis, and the time of progression used in calculation of the survival analysis. Patients will be followed for survival status every 3 months for 2 years after treatment discontinuation or until death, whichever occurs first.

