5.0 STUDY PROCEDURES

Day of each cycle	Screening ¹	On Treatment (1 cycle = 12 weeks) ^{12,13}																		Off Treatment		
		Cycle 1 (±3 days)							Cycle 2 (±3 days)							Cycle 3+ (±3 days)						
		1	15	29	43	57	71	1	15	29	43	57	71	1	15	29	43	57	71	End of Treatment ¹⁴	Follow -Up ¹⁵	
Weeks on study		1	3	5	7	9	11	13	15	17	19	21	23	25	27	29	31	33	35 +			
Assessment or Activity																						
Informed Consent	X																					
Medical history	X																					
Physical exam ²	X	X	X	X	X	X	X	X	X	X	X	X	X	X	X	X	X	X	X	X	X	
ECOG status	X	X	X	X	X	X	X	X	X	X	X	X	X	X	X	X	X	X	X	X	X	
ConMeds	X	X	X	X	X	X	X	X	X	X	X	X	X	X	X	X	X	X	X	X	X	
Adverse events	X	X	X	X	X	X	X	X	X	X	X	X	X	X	X	X	X	X	X	X	X ¹⁵	
Scans ³	X	X ³						X ³								X ³					X	
Lesion Photos ¹⁶	X	X						X								X					X	
CBC with diff ⁴	X	X	X	X	X	X	X	X	X	X	X	X	X	X	X	X	X	X	X	X	X	
Chemistry panel ⁵	X	X	X	X	X	X	X	X	X	X	X	X	X	X	X	X	X	X	X	X	X	
Amylase/Lipase	X	X ⁶						X ⁶								X ⁶					X	
TSH (free T4) ⁷	X	X ⁷						X ⁷								X ⁷						
Pregnancy test ⁸	X	X						X								X					X	
Nivolumab ⁹		T	T	T	T	T	T	T	T	F	F	F	F	F	F	F	F	F				
Ipilimumab ¹⁰		X		X		X		X		X		X		X		X		X				
Tissue collection ¹¹	X	X ¹¹																				
Survival status																					X	

T = 240mg nivolumab

F = 480mg nivolumab

¹ CBC with diff and Chemistry panel should be within 14 days of registration; all other screening procedures should take place within 28 days of registration unless specified otherwise.

² Includes vital signs (pulse, blood pressure), height and smoking history (baseline only) and weight.

³ Imaging must include Chest, Abdomen, and Pelvis as well as a bone scan. Scans may be by CT, PET/CT or MRI (per treating investigator's discretion) with contrast unless strictly contraindicated as well as a bone scan; the same modality used at baseline should be used

throughout. Tumor assessment should be done at screening, cycle 2 day 1 (\pm 1 week) and Day 1 of each cycle (every 12 weeks) thereafter, regardless of dosing schedule until progression or treatment discontinuation whichever occurs later. Tumor assessments will incorporate both RECIST and clinical criteria. Brain MRI is the preferred imaging method for evaluating CNS metastasis, and assessment is only required during screening for eligible subjects with symptomatic CNS involvement.

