6.2 Primary Endpoint

Progression free survival defined as time in months from the date of first study treatment to the date of disease progression or death from any cause, whichever comes first. All patients who receive at least one dose of nivolumab/ipilimumab combination will be included in the primary analyses of PFS. The Response Evaluation Criteria in Solid Tumors (RECIST 1.1) criteria will be used for objective tumor response assessment (when disease is measurable and non-measurable).⁴⁶

- Patients with IBC often do not have measurable disease. For example, patients will sometimes have just recurrent skin involvement, pleural effusions, or bone disease. Measurable disease is not a requirement for enrollment on the study.
- For patients who have only non-measurable disease, unequivocal progression or response will be defined after consideration if the increase in overall disease burden based on the change in non-measurable disease is comparable in magnitude to the increase that would be required to declare PD or tumor response for measurable disease. Complete response will be defined as disappearance of non-measurable disease.
- Clinical and radiological assessments will be performed every 8 weeks (+- 7 days) while on treatment and patients will be followed for up to 2 years after completion of treatment.

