10.2 Sample Size and Accrual

We previously identified 44 patients who were included in a retrospective study of the prognostic significance of HER2 status in IBC. These patients had both HER2 negative and HER2 positive disease, developed metastases, and experienced a disease progression. The median time from the first progression of their metastatic disease to the second progression event or death was approximately 3 months. These patients will be considered our historical control group.

Nivolumab ipilimumab combination will be considered of interest for further study if the median PFS time is increased to at least 6 months. We will test the null hypothesis that median PFS is at most 3 months versus the alternative that it is at least 6 months. The null corresponds to 25% PFS at 6 months under the exponential distribution of PFS versus an alternative 6 month PFS rate of 50%. The null corresponds to 50% PFS at 3 months and the alternative corresponds to 70.71% PFS at 3 months under the same conditions.

We will initially recruit and treat 15 patients. If 7 or fewer initial cohort patients are progression free at 3 months the study will be terminated for lack of efficacy. If at least 8/15 are progression-free at 3 months then we will recruit an additional 14 patients for a total of 29.

The patients free of progression at 3 months from the initial cohort will remain on study until either progression or 6 months evaluation. Second cohort patients will be evaluated at 6 months only. If at least 11/29 patients are progression free at 6 months the null hypothesis will be rejected.

The chance of early study termination (3 months follow up with 15 patients) is 50% under the null and 4.4% under the alternative. Study power is 90% with overall type I error of 7%. The design follows: Early stopping designs based on progression-free survival at an early time point in the initial cohort.⁴⁹

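### Section 4.7 counts responses and progression times after stopping for toxicity with no cut-off at new anticancer therapy, so a later treatment's effect can be credited to nivolumab/ipilimumab

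*Combined protocol and SAP*

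**What the plan says.** Section 4.7 covers patients who stop for unacceptable adverse events without progression. They are "followed with imaging studies every 8 weeks until the time of progression radiographically according to RECIST 1.1 criteria". On what such imaging may show, the plan rules: "In the event that a radiographic response is detected, then this event will be included as a response in the final analysis". For the time-to-event results, the same sentence goes on to have the later date count: "and the time of progression used in calculation of the survival analysis". Progression is the only end point given for this imaging.

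The same section does use new therapy as a limit, but only for adverse-event follow-up: "or until the patient starts a new treatment, whichever occurs first". Footnote 14 of the section 5.0 schedule uses it again, for the timing of the End of Treatment visit.

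Section 6.2 defines PFS as "time in months from the date of first study treatment to the date of disease progression or death from any cause, whichever comes first". The final rule in 10.2 is: "If at least 11/29 patients are progression free at 6 months the null hypothesis will be rejected". The restriction on other anticancer drugs in 4.5.2 begins: "Subjects are prohibited from receiving the following therapies during the Screening and Treatment Phase of this trial". It does not reach the off-treatment period.

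**The concern.** Sections 1.3.1 and 10.1 justify the window design by the wish to see immunotherapy act before other systemic treatment for metastatic disease has been given. Under 3.1.5 and 3.2.2, patients have had no chemotherapy in that setting. A patient who stops the study drugs for toxicity may therefore start a first chemotherapy while still progression-free.

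As written, scans made on that chemotherapy still feed the efficacy results. A response confirmed on it would count in ORR and CBR. Remaining progression-free on it would count at 3 or 6 months. With one arm compared against a historical median of about 3 months, no control group shares this bias. If the later therapy is more active than the null, the bias is upward. It would also arise in the patients who tolerated the study drugs least.

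**Working it through.** **1. Is a cut-off supplied anywhere?**
- 4.7: new therapy ends adverse-event follow-up only.
- 4.5.2: the restriction covers screening and treatment only.
- 5.0, footnote 3: scans run "until progression or treatment discontinuation whichever occurs later". Footnote 15 has progression documented for up to 2 years off treatment. Neither mentions new therapy as a limit on efficacy data.
- 6.2: PFS ends at progression or death.
- 6.6.3: the best-response window closes at progression or recurrence.
- 6.7: evaluability needs one post-baseline scan.
- 10.2: the counts have no rule for switchers.
- 10.3: Kaplan-Meier with no censoring rules. The intention-to-treat paragraph covers ineligibility and the amount of study drug, not later therapy.

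No efficacy cut-off exists.

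**2. Reproduce the design (10.2).** Let p3 and p6 be the 3- and 6-month progression-free rates. X ~ Bin(15, p3), and the trial continues if X ≥ 8. Given X, Y ~ Bin(X, p6/p3). Second cohort: Z ~ Bin(14, p6). Reject if Y + Z ≥ 11.
- Null (0.50, 0.25): early stop 50.0%, rejection 7.0%.
- Alternative (0.7071, 0.50): early stop 4.4%, rejection 90.1%.

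These match the stated 50%, 7%, 4.4% and 90%.

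**3. Illustrate the effect under the null.** Assumptions, none given by the documents: a fraction f of patients is on a stop-and-switch path. They progress at the null hazard (median 3 months) until week 10, t = 10/4.345 = 2.30 months. Those still progression-free then switch to a therapy with median PFS M.

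For switch-path patients, S(3) = 2^−(2.30/3 + 0.70/M) and S(6) = 2^−(2.30/3 + 3.70/M).
- M = 6: S(3) = 0.542, S(6) = 0.383.
- M = 12: S(3) = 0.564, S(6) = 0.475.
- M = 3: S(3) = 0.50, S(6) = 0.25, the null itself.

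Then p3 = (1−f)(0.50) + f·S(3) and p6 = (1−f)(0.25) + f·S(6), entered in step 2.

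| f | M = 3 | M = 6: p3, p6 → rejection | M = 12: p3, p6 → rejection |
|---|---|---|---|
| 10% | 7.0% | 0.504, 0.263 → 9.4% | 0.506, 0.272 → 11.3% |
| 20% | 7.0% | 0.508, 0.277 → 12.3% | 0.513, 0.295 → 16.9% |
| 28% | 7.0% | 0.512, 0.287 → 14.9% | 0.518, 0.313 → 22.0% |

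Only 2^−(2.30/3) = 59% of the switch-path patients reach week 10 without progression, so those who actually switch are about 0.59f of all patients.

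**4. Sensitivity to switch time**, with f = 10–30% and M = 6–12 months. A switch at 3 months gives 8.8–17.9%. A switch at 1.5 months gives 10.3–31.8%.

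**5. Cost of counting switchers as failures.** Under the alternative, suppose a fraction f of otherwise progression-free patients has switched. If they fail at both looks, use p3 = 0.7071(1−f) and p6 = 0.50(1−f). If they fail at 6 months only, keep p3 = 0.7071.
- f = 10%: power 75% (both looks) or 81% (6 months only).
- f = 20%: 53% or 64%.
- f = 28%: 35% or 48%.

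**The case against.** Several points on the other side stand.

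- **Treatment policy.** Following PFS through later therapy can be a deliberate choice, and it sits comfortably with 10.3, which analyses everyone whatever amount of study drug they received. But the plan does not declare it for new therapy. It also would not isolate the study drugs' effect against a historical median, and it is hard to defend for ORR and CBR.
- **Borrowed inputs.** The 10% in 1.2.4 is discontinuation on ipilimumab 3 mg/kg in melanoma. The 28% is the grade 3–4 event rate for a similar schedule in lung cancer. A reader might take 28% as a stopping rate, but 4.3.2 exempts many grade 3 events and allows only the attributed drug to be stopped.
- **Later-therapy activity.** The only IBC figure in 10.2 is about 3 months from first to second progression or death, and at that median there is no inflation. First-line therapy may do better, but the documents give no figure.

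A reader might also infer a much larger error by giving switchers the later therapy's full PFS rates from day 0. With 85%/70% at 3/6 months and f = 28%, that gives 49%. The documents do not support it: the 4.7 rule applies only to patients who have not progressed when they stop, so they face the study-drug hazard first.

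Nor would one partial response on a later scan make a patient a responder. Section 6.6.3 requires confirmation, and 6.1 schedules the confirmatory scan 8 weeks later. A response before 6 months also does not show progression-free status at 6 months.

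**Conclusion.** The gap holds. Section 4.7 affirmatively counts off-treatment responses and later progression times, and nothing elsewhere stops that at new anticancer therapy. ORR, CBR, PFS and both decision counts are exposed.

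How far is not known from the documents. The step 3 results rest on an assumed week-10 switch, an assumed fraction and assumed later-therapy medians. They range from no inflation to about 22%, and show that a modest number of switchers could matter to a rule with a nominal 7% error. They are not a forecast. The need for a rule does not depend on them.

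**What to change.** 1. In 4.7 and 6.6.3, state that only assessments made before the start of any new anticancer therapy count toward best overall response, ORR and CBR.
2. Record the start date of new anticancer therapy. The data submission guidelines are a separate document (11.4), so whether this is already collected cannot be judged here.
3. In 6.2, 10.2 and 10.3, prespecify one handling of patients who start new therapy without documented progression, and apply it to both the Kaplan-Meier PFS and the 3- and 6-month counts. Either the switch counts as not progression-free, or follow-up continues through the new therapy. Report the other as a sensitivity analysis. Censoring switchers in Kaplan-Meier while failing them in the counts would give one endpoint two rules.

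The cost is wording in five sections and at most one data field, with no added patients or scans. The downside is real: ORR and the counts may be less favourable. If switchers count as failures in the primary rule, 10.2 must state the power loss shown in step 5 rather than leave 90% standing.

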1.2 Intervention Background & Overview

1.2.1 Nivolumab, ipilimumab and nivolumab/ipilimumab combination

Nivolumab (BMS-936558, MDX-1106) is a fully human monoclonal immunoglobulin G4 (IgG4) antibody (HunMab) that is specific for human programmed death-1 (PD-1, cluster of differentiation 279 [cd279]) cell surface membrane receptor (Investigator brochure version 2014). PD-1 is a negative regulatory molecule that is expressed transiently following T-cell activation and on chronically stimulated T cells characterized by an “exhausted” phenotype. Nivolumab anti-tumor activity has been investigated in patients with melanoma, non-small cell lung cancer (NSCLC), and renal cell carcinoma (RCC).³⁰⁻³² The combination of nivolumab and ipilimumab (anticytotoxic T lymphocyte associated antigen-4 [anti-CTLA-4]) in phase 1/2 trial showed markedly enhanced clinical activity with acceptable safety profile in melanoma patients.³³ Nivolumab is currently FDA approved for BRAF V600 mutation-positive unresectable or metastatic melanoma, as a single agent., unresectable or metastatic melanoma, in combination with ipilimumab., metastatic non-small cell lung cancer and progression on or after platinum-based chemotherapy and Advanced renal cell carcinoma who have received prior anti-angiogenic therapy, the treatment of patients with advanced stage non-small cell lung cancer after progression on platinum based chemotherapy and patients with metastatic renal cell carcinoma. Nivolumab is well tolerated when compared to chemotherapy with rare grade 3 or 4 toxicities. Nonetheless is has been associated with immune related adverse events such as pneumonitis, colitis, which have frequency of less than 5%.³⁰

Ipilimumab is a human immunoglobulin G (IgG1)κ anti-CTLA-4 monoclonal antibody. Several preclinical studies demonstrated that CTLA-4 blockade could augment T cell-mediated immune responses against tumors.^{34,35} This led to the development of ipilimumab, a fully humanized IgG1 monoclonal antibody to CTLA-4. Two phase 3 trials demonstrated a durable clinical benefit for approximately 20-25% of metastatic melanoma patients with ipilimumab resulting in FDA approval of this compound as a first and second-line agent in metastatic melanoma.^{36,37} Ipilimumab has been associated with immune mediated toxicities such as diarrhea, colitis, rash, pruritus, hypothyroidism. The risk of grade 3 and 4 immune-related adverse is estimated at approximately 14%.³⁶

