2.2 Secondary Objectives & Endpoints

2.2.1 To assess the overall response rate (ORR) and clinical benefit rate (CBR) according to RECIST criteria v1.1, in patients with recurrent IBC treated with nivolumab and ipilimumab

Overall response rate (ORR) is defined as Complete Response (CR) + Partial Response (PR). Clinical benefit rate (CBR) is defined as CR + PR + Stable Disease (SD). Patients will have scans every 12 weeks.

2.2.2 To assess overall survival in patients with recurrent HER2 negative IBC treated with nivolumab and ipilimumab.

Patients will be followed from the start of treatment until 2 years post-treatment or death, whichever occurs first, and average survival time will be measured.

2.2.3 To assess the safety and tolerability of nivolumab and ipilimumab in patients with recurrent IBC according to the National Cancer Institute Common Terminology Criteria Adverse events v 4.03).

The number, frequency, and severity of adverse events will be collected from time of consent until 12 weeks after study treatment.

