¹⁴ End of Treatment visit will occur 30 days (\pm 7 days) after stopping nivolumab or combination treatment, or before the patient starts new treatment, whichever occurs first. Adverse events will be recorded for up to 12 weeks after stopping treatment.

¹⁵ Patients will be followed and assessed for adverse events every 4 weeks (\pm 7 days) by routine clinic visit for the first 12 weeks after treatment. Thereafter, patients will be followed (either by routine clinic visit or by phone) every 3 months for up to 2 years while off treatment to document survival and disease progression.

¹⁶ Photographs for disease assessments will be taken by study staff on a study-supplied digital camera. It is preferred that these photos be taken on a white background (wall of patient room) using a ruler measurement when possible. Photographs should not include any identifying characteristics

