10.3 Data Analyses Plans

Response rates and 95% confidence intervals will be calculated using exact binomial probability distributions. Progression-free survival and overall survival will be analyzed using Kaplan-Meier curves. Adverse events will be summarized descriptively using frequencies and percentages. Statistics will be given on type, severity, frequency and attribution of adverse events. Sample size considerations are described above.

An intention to treat analysis will be done. In a single group Phase II study, intention to treat means that all patients who are evaluated and registered for the study are followed and analyzed regardless of (a) whether they were subsequently found to be protocol ineligible and (b) the amount of study treatment (nivolumab/ipilimumab) they received. To calculate progression-free and overall survival in patients who received nivolumab/ipilimumab, times will be taken from the time of study registration. This definition parallels the definition of intention to treat in randomized clinical trials.

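### Survival follow-up ends 2 years after each patient's own treatment stop, so OS censoring after month 24 is potentially informative and the late Kaplan-Meier curve is not reliable

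*Combined protocol and SAP*

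**What the plan says.** Three places tie the end of survival follow-up to the individual patient's treatment stop. Section 4.7: "Patients will be followed for survival status every 3 months for 2 years after treatment discontinuation or until death, whichever occurs first". Section 2.2.2, which also names the summary to be reported: "until 2 years post-treatment or death, whichever occurs first, and average survival time will be measured". Footnote 15 of the schedule in 5.0: "every 3 months for up to 2 years while off treatment to document survival and disease progression".

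Treatment itself is open-ended. Under 4.6, "treatment may continue until one of the following criteria applies", and the list is progression, intercurrent illness or unacceptable adverse events. Footnote 12 in 5.0 adds withdrawal of consent. No maximum number of cycles is given.

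Section 6.3 measures OS from first study treatment to death. Section 10.3 says "Progression-free survival and overall survival will be analyzed using Kaplan-Meier curves", but takes the times from registration. No OS censoring rule, data cut-off date or sensitivity analysis is stated.

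**The concern.** Kaplan-Meier requires that patients censored at a given time have the same later death risk as those who remain under observation. Here the planned censoring time is a function of a prognostic event after baseline. A patient who progresses and stops at month 3 is censored at 3 + 24 = month 27. A patient who stops at month 30 is followed to 30 + 24 = month 54. From month 24 on, early progressors who are still alive leave the risk set, and the curve is carried by patients who stayed on treatment longer.

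OS is a named secondary endpoint of a single-arm trial with no internal comparator, so a late plateau could be read as an immunotherapy survival tail. The average survival time in 2.2.2 is more exposed still, because a mean depends on the tail of the curve.

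**Working it through.** **The plan's own figures.** The documents give no figure for OS. The PFS design can be checked: X1 ~ Bin(15, p3), stop if X1 ≤ 7; then Bin(X1, p6/p3) + Bin(14, p6), reject if the total is ≥ 11. With p3/p6 = 0.50/0.25 the early-stop probability is 50.0% and the type I error 7.01%. With 0.7071/0.50 they are 4.37% and power 90.1%. All match 10.2, and this point does not touch them.

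**Inputs.** From the documents: censoring at treatment stop + 24 months (2.2.2, 4.7, footnote 15); median PFS 3 or 6 months, exponential (10.2); 29 patients. Assumed and varied, because the documents are silent: post-progression survival, and any subgroup with durable control. Section 1.2.1 mentions "durable clinical benefit for approximately 20-25% of metastatic melanoma patients" for ipilimumab, but that is a different disease. The model takes treatment stop T as progression and OS = T + P, where P is post-progression survival. The censoring time is C = T + 24.

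**Up to month 24.** C is never below 24, so this rule censors nobody earlier. Kaplan-Meier minus truth is 0.000 at month 24 in every scenario.

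**Worked scenario.** 20% durable (median PFS 36 months), 80% with median PFS 2.5 months, post-progression median 18 months, all exponential. For rates a (PFS) and b (post-progression), S(t) = (a·e^(-bt) − b·e^(-at)) / (a − b).

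- Month 24: durable 0.863, others 0.461; mixture 0.2 × 0.863 + 0.8 × 0.461 = 0.541.
- Month 36: durable 0.750, others 0.290; mixture 0.150 + 0.232 = 0.382.
- Month 48: durable 0.636, others 0.183; mixture 0.127 + 0.146 = 0.274.

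Simulated Kaplan-Meier under the censoring rule (400,000 patients) gives 0.541, 0.426 and 0.373. The bias is 0, +4.4 and +9.9 points.

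The risk set explains why. At month 36 only patients with T > 12 are still observed. For exponential T, P(T > 12, OS > 36) = P(T > 12) × S(24).

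- Durable: 0.2 × 0.794 × 0.863 = 0.137.
- Others: 0.8 × 0.036 × 0.461 = 0.013.
- Durable share of those observed: 0.137 / 0.150 = 91%.
- Durable share of those truly alive: 0.150 / 0.382 = 39%.
- Expected number at risk: 29 × 0.150 = 4.4.

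**Range over assumptions** (Kaplan-Meier minus truth, in points)

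| Assumption | Month 36 | Month 48 |
|---|---|---|
| Single exponential PFS, median 3 or 6; constant independent post-progression hazard | 0 to about +0.5 | 0 to about +1.3 |
| PFS and post-progression survival correlated (gamma frailty, variance 0.5-1; post-progression median 12-18) | +1.7 to +3.3 | +4.1 to +7.2 |
| 10-20% durable (median PFS 48), others 3-5; post-progression median 9-18 | +1.6 to +3.8 | +3.8 to +9.0 |
| 20% durable (median PFS 36), others 2.5-4; post-progression median 6 | +1.5 to +2.0 | +2.5 to +2.9 |
| 20% durable, others 3; falling post-progression hazard (Weibull shape 0.5-0.75, median 12-18) | +1 to +2 | +2 to +6 |
| No durable subgroup; falling post-progression hazard (Weibull shape 0.5-0.75) | −0.5 to −1.4 | −1.3 to −4.1 |

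The last row reverses because the patients dropped are more than 24 months past progression. By then their hazard is lower than that of the patients who stay.

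**At n = 29** (20% durable, 3 months in the rest, post-progression median 18): mean Kaplan-Meier is 0.427 against a true 0.389 at month 36, and 0.369 against 0.277 at month 48. The biases are +3.8 and +9.2 points. The sampling SD is about 11 and 12 points.

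**With a common cut-off.** Censoring all patients at one time (48 or 60 months from start) gives a difference of 0.000 at every earlier time point.

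**The case against.** A reader might infer that the rule simply overstates late survival. The documents do not support that as a certainty. They give no post-progression survival and no link between PFS and later survival. Under the protocol's own exponential planning model, with a constant independent post-progression hazard, there is almost no bias, and a falling hazard without a durable subgroup reverses it. The larger figures need a durable subgroup, and the only such percentage in the documents comes from melanoma. Section 1.1 calls the prognosis of metastatic IBC dismal; short post-progression survival shrinks the bias. This objection stands, and it limits the claim to a potential, probably upward, bias.

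A reader might also infer that the median is inflated. An overstatement of about 4 to 8 months appears only when the true median OS is 34 to 37 months. Below about 30 months the median hardly moves, and below 24 months not at all.

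Timing matters too. At 2 patients a month (section 3.0), with an assumed 3-month pause after stage 1, the 6-month read-out falls at 7.5 + 3 + 7 + 6 = 23.5 months. Section 11.8 asks for a data summary within 3 months of primary completion. In that summary, ordinary calendar censoring dominates, so the rule matters only in a later OS report. The plan does not exclude one, and its follow-up schedule is built to supply the data.

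The month-27 example is simplified. Section 4.4 allows treatment to continue until progression is confirmed, so the stop, and with it the censoring, can come about 3 months later. The dependence on progression remains.

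Finally, OS is secondary with no hypothesis test, and sampling error at 36 and 48 months exceeds the bias. That lowers the priority. It does not make the late curve reliable.

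**Conclusion.** The point holds in a limited form. The wording of the follow-up rule is clear and consistent in three places. It makes OS censoring after month 24 depend on time to treatment stop, so independent censoring is not secured there. That progression drives most stops is an inference from the planned median PFS of 3 to 6 months, though a natural one.

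The bias is probably upward if a durable-control subgroup exists: about +1.5 to +4.5 points at 36 months and +3 to +10 at 48, assuming 10-20% durable and a post-progression median of 6-18 months. It is near zero, or about 1 to 4 points negative, under other assumptions that the documents do not exclude.

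PFS, the 11/29 decision rule, OS to 24 months and any median below 24 months are untouched. This is a cheap improvement to a secondary endpoint, not a defect in the primary analysis.

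**What to change.** In 10.3, limit formal OS estimates to 24 months: the 12- and 24-month rates, and the median if it is reached by then. State a single time origin, reconciling registration in 10.3 with first treatment in 6.3. Label any later curve as descriptive and potentially informatively censored. In 2.2.2, replace the average survival time with these summaries.

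If OS beyond 24 months is wanted, amend 2.2.2, 4.7 and footnote 15 so that survival status is collected for every patient to one common cut-off date, whenever treatment stopped.

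The first option needs a few sentences and no new data, since every treated patient already has at least 24 months of planned survival follow-up. It gives up formal OS claims past 24 months, where few patients remain at risk (about 4 to 7 of 29 at month 36 in scenarios with 20-25% durable control). The second option costs some additional phone contacts.
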